A prospective, 2-group, single-blind, randomized clinical trial design is planned. The design will allow us to test the impact of the NO-ASPIRATE intervention on outcomes of microaspiration and VAC.

Aims and Hypotheses

Our primary aim is to compare the effects of the NO-ASPIRATE intervention versus usual care on microaspiration in critically-ill intubated patients on MV. Patients often have high volumes of oropharyngeal secretions, and despite existing interventions, microaspiration occurs. Regular removal of secretions that accumulate in the oropharynx is intended to decrease the volume or potential load, and thus reduce microaspiration. Our working hypotheses are that subjects in the NO-ASPIRATE group will have a reduction in microaspiration as measured by the percentage of tracheal specimens that are positive for α -amylase (1.1) and *mean values of α -amylase* (1.2).

A secondary aim is to compare the effects of the NO-ASPIRATE intervention on development of VAC and duration of VAC-free days. By reducing the risk for microaspiration, VAC should be reduced. Our working hypotheses are that the subjects in the NO-ASPIRATE group will have a lower rate of VAC (2.1) and longer duration of VAC-free days (2.2). Another secondary aim is to explore changes in the ratio of α -amylase in the tracheal aspirate versus the mouth over time. Our working hypothesis is that subjects in the NO-ASPIRATE group will have a lower tracheal/oral α -amylase ratio over time (3.1).

Setting and Sample

Setting. The study will be conducted in the ICUs at Orlando Regional Medical Center (ORMC), a division of Orlando Health. ORMC is an 808-bed tertiary care facility that specializes in trauma, emergency care, cardiology, orthopedics, neurosciences, and internal medicine. The hospital serves a 5-county area in Central Florida area with a diverse population of 2.8 million people.¹¹⁹ The ICUs include Trauma (14 beds), Neuroscience (16 beds), Multi-System (10 beds), and Cardiac (10 beds). Nursing and respiratory care practices for airway management are standardized across units. The patients are managed by a team of either

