Endpoints. The intervention will be delivered per protocol until one of the following endpoints is met (whichever occurs first): 1) ETT removed (extubation); 2) tracheostomy performed; 3) 14 days of enrollment; or 4) other exclusion criterion met (e.g., rescue ventilation). *Extending the intervention to 14 days will allow us a better opportunity to address the secondary aim of VAC. At the study site, the median time to tracheostomy is 8 days; 85% of patients on prolonged MV undergo a tracheostomy by Day 14.*¹¹² *This duration of enrollment is longer than that reported in other intervention studies,*^{19,73,109} *and will allow us to test the effect of the intervention on both microaspiration and VAC prevention for an extended period. Subjects must be enrolled at least 36 hours to be included in analysis. Since the duration of MV varies and we want to assess the effect of our intervention on preventing microaspiration, we determined (with input from consultants) that a minimum enrollment of 36 hours would provide adequate samples to address the primary aim.*

Measurement of Primary and Secondary Outcome Variables

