VAC. VAC will be determined using the CDC/NHSN criteria (Figure 6, blue boxes).¹⁶ We will assess ventilator data (FiO₂ and PEEP) daily from the medical record to assess for worsening oxygenation status. Per consultation with [name], we will assess for VAC for 2 days beyond the last intervention. To address Aim 2 and hypotheses 2.1 and 2.2, we will record VAC as positive or negative. We will also record the time to VAC in days (0.1 day increments). Determination of VAC will be made by our intensivist co-investigator. The CDC/NHSN algorithm proceeds to determine if VAC is infection-related (grey part of algorithm).¹⁶ *Our primary endpoint is VAC as a broad complication that includes both infectious and noninfectious etiologies; however, we will also report possible and probable VAP in our analyses as applicable.*

Tracheal/Oral Ratio of α -Amylase. To address Aim 3 and hypothesis 3.1, the ratio of the tracheal value to the oral value of α -amylase for each paired sample will be calculated.

Training and Data Management

Personnel Training and Fidelity. The PI will be responsible for training and will be assisted by the PD in ensuring that all personnel are knowledgeable in their roles. At the beginning of the study, the PI and PD will develop a comprehensive study Operations Manual, which will include procedures and checklists for subject enrollment, delivery of the NO-ASPIRATE and usual care/sham interventions, data collection, and ongoing

reporting related to the study (e.g., IRB and DSMB). All study personnel will complete the required CITI training on protection of human subjects and will sign confidentiality agreements.

The PI and PD will train the RAs in all study-related procedures. Initial training for the NO-ASPIRATE intervention, the usual care/sham intervention, and specimen collection will be conducted in a simulation laboratory, followed by observation in the clinical setting. Inter-rater reliability will be established for delivery of the NO-ASPIRATE and usual care/sham interventions, and for review of the medical record for study-related data. A kappa of at least .90 will be achieved between data collectors. To ensure treatment fidelity, additional re-assessment and related training will be done every 6 months using a standard observation checklist.

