Aim 2. To evaluate the NO-ASPIRATE intervention versus usual care on VAC rate and time to occurrence.

Hypothesis 2.1. Subjects in the NO-ASPIRATE group will have a significantly lower rate of VAC as compared to those in the usual care group. **Analysis 2.1.** Percentages of VAC for both groups will be computed. The percentage difference between the two groups will be calculated along with the 95% confidence interval for the percentage difference. The logistic regression including covariates of interest will be used to assess the percentage difference adjusting for the prognostic covariates. **Hypothesis 2.2.** The number of VAC-free days will be longer in those in the NO-ASPIRATE group as compared to the usual care group.

Analysis 2.2. Time to VAC event for both the NO-ASPIRATE and the usual care groups will be assessed using the Cox proportional hazard model.¹²⁶ The hazard ratio and the 95% confidence interval of the hazard ratio of NO-ASPIRATE group versus the usual care group will be computed. The graphical display of the Kaplan-Meier estimators for both groups will be presented.¹²⁷ The Cox proportional hazard model with prognostic covariates of interest will be used to assess the difference adjusting for the prognostic covariates.

Aim 3. To explore changes in the tracheal-to-oral α -amylase ratio between groups over time.

Hypothesis 3.1. Subjects in the NO-ASPIRATE group will have a significantly lower tracheal/oral α -amylase ratio over time as compared to those in the usual care group. **Analysis 3.1.** Treatment effect on reducing tracheal/oral salivary amylase ratio over time will be assessed by the generalized linear models using the generalized estimating equation (GEE) method.^{124,125} In addition, the generalized linear models adjusting for prognostic covariates will be used to assess ratios over time adjusting for prognostic covariates.

Solutions to Potential Issues

Design. We are planning a single-blind RCT to test the NO-ASPIRATE intervention. Our goal is to blind the staff and subjects to the intervention group by using a sham treatment for those in the usual care group, which we believe to be a strength. Despite our efforts, knowledge of group membership may be identified.

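### Analysis 2.2 has no rule for extubation, tracheostomy or death: if these exits are censored, Kaplan-Meier overstates VAC incidence, and the VAC-free days named in H2.2 are neither defined nor compared

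*Combined protocol and SAP*

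**What the plan says.** The Aims and Hypotheses section sets a secondary aim to "compare the effects of the NO-ASPIRATE intervention on development of VAC and duration of VAC-free days". In Data Analysis, Hypothesis 2.2 reads "The number of VAC-free days will be longer in those in the NO-ASPIRATE group as compared to the usual care group". The Aim 2 heading above it is worded differently: "To evaluate the NO-ASPIRATE intervention versus usual care on VAC rate and time to occurrence".

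Analysis 2.2 then states: "Time to VAC event for both the NO-ASPIRATE and the usual care groups will be assessed using the Cox proportional hazard model". A hazard ratio with a 95% confidence interval follows, then "The graphical display of the Kaplan-Meier estimators for both groups will be presented", then a covariate-adjusted Cox model. There is no censoring rule and no mention of competing events.

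Other sections fix when a subject can be seen to have VAC:

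- **VAC paragraph (Measurement of Primary and Secondary Outcome Variables):** VAC is determined from daily FiO2 and PEEP, assessed until 2 days after the last intervention. For H2.1 and H2.2 it is recorded as yes or no, with time to VAC in tenths of a day. No VAC-free-days variable is defined.
- **Endpoints:** the intervention stops at extubation, tracheostomy, 14 days, or another exclusion criterion, whichever is first.
- **Analysis 2.1:** separately reports the percentage with VAC in each group, and the difference with a 95% confidence interval.

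**The concern.** VAC is a worsening in ventilator settings after a stable period on the ventilator. A subject who leaves the ventilator or dies without VAC can no longer have it. These are competing events, not losses to follow-up. Kaplan-Meier with such subjects censored treats them as if they would have gone on to VAC at the same rate as those still ventilated. Its complement then estimates VAC risk in a setting where nobody leaves the ventilator or dies.

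Tracheostomy is different. It ends the intervention, and VAC assessment 2 days later, but the patient may stay ventilated and at risk. Censoring there is possibly informative, but it is not a competing event in itself.

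Two things are at stake. The published curves could show a VAC risk far above the percentages reported beside them. And a reader who takes the Cox result as the answer on VAC-free days could be misled, because that quantity also depends on how fast subjects are extubated and how many die.

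**Working it through.** The plan gives no event count, hazard ratio or power for H2.2, so there is no figure of its own to reproduce. What follows is an illustration.

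**Inputs**
- Site ventilation: median 4 days, mean 6.2 days (Setting and Sample, fiscal year 2012, all ventilated patients on the study units).
- Horizon: 14 days (Endpoints).
- At least 36 hours of expected intubation after enrollment, and at least 36 hours enrolled to be analysed (Setting and Sample; Endpoints).
- VAC assessed for 2 days after the last intervention (VAC paragraph).
- Assumed, not in the documents: VAC hazard h of 0.01 to 0.05 per day, with constant hazards.

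**1. Kaplan-Meier against cumulative incidence.** The exit hazard is c = ln 2 / 4 = 0.173 per day. With exits censored, 1-KM at day 14 is 1 − exp(−14h). If no exit can occur before day d, the cumulative incidence is

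CIF = 1 − exp(−hd) + exp(−hd) × h/(h+c) × [1 − exp(−(h+c)(14−d))].

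Three values of d cover the ways of treating the entry and follow-up rules: d = 0 ignores both, d = 1.5 applies the 36-hour minimum, and d = 3.5 adds the 2 further days of assessment.

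For h = 0.03: 1-KM = 1 − exp(−0.42) = 34.3%. With d = 0, CIF = 0.03/0.2033 × [1 − exp(−2.846)] = 0.1476 × 0.942 = 13.9%. With d = 1.5, CIF = 0.044 + 0.956 × 0.1476 × 0.921 = 17.4%. With d = 3.5, CIF = 0.0997 + 0.9003 × 0.1476 × 0.882 = 21.7%.

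| h per day | 1-KM, day 14 | CIF, d = 0 | CIF, d = 1.5 | CIF, d = 3.5 | 1-KM ÷ CIF |
|---|---|---|---|---|---|
| 0.01 | 13.1% | 5.0% | 6.3% | 7.9% | 2.6 to 1.6 |
| 0.03 | 34.3% | 13.9% | 17.4% | 21.7% | 2.5 to 1.6 |
| 0.05 | 50.3% | 21.4% | 26.7% | 33.1% | 2.4 to 1.5 |

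The direction does not depend on these assumptions: when competing events are censored, 1-KM cannot fall below the cumulative incidence. The size does depend on them.

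**2. Does the hazard ratio determine VAC-free days?** Take a total exit hazard of 1/6.2 per day, an assumed control VAC incidence of 20% by day 14 (which gives a VAC hazard of 0.0434), and assume that 20% of exits without VAC are deaths. Count the days before a first VAC or death up to day 14, with subjects extubated alive credited to day 14. With v, x and m the hazards of VAC, extubation and death, L = v + x + m and q = 1 − exp(−14L), the mean is q/L + x(14/L − q/L²).

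| Scenario | VAC hazard ratio | Mean VAC-free days |
|---|---|---|
| Control | – | 10.5 |
| VAC hazard lowered, nothing else changed | 0.6 | 11.2 |
| Extubation 1.5 times faster | 1.0 | 11.1 |
| Death hazard halved | 1.0 | 11.1 |
| VAC hazard lowered, death hazard 1.5 times | 0.8 | 10.3 |

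A hazard ratio of 1.0 can go with more VAC-free days than control, and a favourable ratio of 0.8 with fewer. The two are different quantities.

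**The case against.** The strongest reply is that the plan never says these exits are censored. That is correct. A reader might infer that the plan treats extubation and death as ordinary censoring, but the text is silent, and censoring is only the default for a Cox and Kaplan-Meier plan whose observation ends there. If subjects extubated alive were instead carried VAC-free to day 14, extubation would cause no inflation and most of the gap above would vanish.

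A reader might also infer that the trial's VAC risk estimates are inflated in both arms. The documents do not support that. Absolute risk comes from the percentages in Analysis 2.1, which this does not touch. The Kaplan-Meier curve is a display, and nothing says that risk will be read from it. Nor is the Cox model wrong: where the VAC hazard is equal and one arm extubates faster, a ratio of 1 is the right answer about the VAC hazard, and the lower crude rate would show in Analysis 2.1.

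Third, the VAC paragraph and the Aim 2 heading both point to time to VAC as the intended measure, so the mismatch with H2.2 is largely one of wording. I accept this, and rewording is an adequate remedy. It goes too far to say that nothing relevant to H2.2 is analysed.

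Fourth, one might fault the Endpoints list for omitting death. That list says when the intervention stops, not which events enter the analysis. The gap is the missing analysis rule.

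Fifth, the 4-day median describes all ventilated patients, not those who would be enrolled. This is why the range with d = 1.5 and d = 3.5 is shown. The ratio shrinks, but stays above 1.5.

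**Conclusion.** The point holds in a limited form. Analysis 2.2 leaves out how extubation, tracheostomy and death are handled, for an outcome that can arise only on the ventilator. Under the default reading, 1-KM overstates cumulative VAC incidence and will disagree with Analysis 2.1. At an assumed VAC hazard of 0.03 per day the illustration is 34% against 14% to 22%, a ratio of about 1.6 to 2.5. This rests on constant hazards, an assumed VAC rate, site-wide ventilation times, and exits being censored.

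Separately, and without any modelling, H2.2 names VAC-free days, which the plan neither defines nor compares. The Cox hazard ratio is interpretable as cause-specific but cannot stand in for them. H2.2 is secondary, so the primary conclusion is unaffected.

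**What to change.** In Analysis 2.2:

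1. Replace the Kaplan-Meier display with Aalen-Johansen cumulative incidence curves by group, with liberation from the ventilator without VAC, and death, as competing events. State that tracheostomy subjects are censored at the end of VAC assessment unless they are off the ventilator, and note that this censoring may be informative.
2. Keep the Cox model and label its hazard ratio cause-specific. Gray's test or a Fine-Gray estimate is optional.
3. Either reword H2.2 as time to VAC, to match the VAC paragraph and the Aim 2 heading, or define VAC-free days (time window, and rules for death, extubation and tracheostomy) and compare the groups on it directly. The second choice must also say how days after VAC assessment has ended are counted.

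The cost is a few sentences of plan text and standard code. It is not quite free on data: Table 1 lists ventilator days and length of stay but no date of death, so that must be added to the extraction from the medical record. Settle this before any unblinded analysis.
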